After the short-term follow-up visit, all participants will enter the long-term follow-up period (Visit 802-8XX). Long-term follow-up begins the day after the short-term follow-up visit is completed and continues until participant's death, withdrawal from study, or study completion. Long-term follow-up visits should occur approximately every 2-3 months (Q60-90D). Tumor assessments should continue approximately every 3 months during follow-up for participants without evidence of disease progression at the time of treatment discontinuation.

Table JP04.1. Baseline Schedule of Activities

Procedure	Day relative to C1D1		Instructions
	≤28	≤14	
Informed consent	X		
 Must be signed prior to conducting any protocol-specific tests/procedures Minor participants must be re-consented if they reach the age of majority during the course of the study.
Inclusion/exclusion criteria	X		
 Confirm prior to randomization
Randomization	X		
Demographics	X		
 Include race, gender, ethnicity, and birth date per local regulations.
Preexisting conditions and medical history, including relevant surgical history	X		
 Include Ewing's sarcoma or Ewing's sarcoma-like fusion genes, if known CCI
Prior and current treatments for Ewing's sarcoma	X		
 Record prior anticancer therapy
Substance use (alcohol and tobacco)	X		
Concomitant medications	X		
 Record all premedication, supportive care, and concomitant medication See Section 3.7.6
Adverse events	X		
 CTCAE Version 5.0
Height, weight, and body surface area	X		
Vital signs	X		
 Temperature, blood pressure, pulse rate, and respiratory rate
Physical examination	X		
 Includes respiratory auscultation
CCI	X		
 CCI
Performance status	X		
 Lansky for age <16 years Karnofsky for age ≥16 years

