3.7.6. Concomitant Therapy

No other chemotherapy, investigational medications, immunotherapy, hormonal cancer therapy, herbal supplements and/or herbal drugs intended to treat cancer will be permitted while participants are on study treatment.

Palliative radiation and surgery for cancer may be allowed after discussion with the Lilly CRP.

A list of restricted and excluded concomitant therapies and exceptions is provided in [Attachment 5](#). All premedication, supportive care, and concomitant medication must be reported on the CRF at each visit.

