3.10.2. Populations for Analysis

The following analysis sets will be defined for this study:

Intention-to-treat (ITT) analysis set: will include all randomized participants. The ITT analysis of efficacy data will consider allocation of participants to treatment groups as randomized and not by actual treatment received. This analysis set will be used for all baseline and efficacy analyses.

Safety analysis set: will include all randomized participants who received any quantity of study treatment, regardless of their eligibility for the study. The safety evaluation will be performed based on the first doses of study treatment a participant actually received, regardless of the arm to which he or she was randomized. The safety analysis set will be used for all dosing/exposure, safety, and resource utilization analyses.

Pharmacokinetic analysis set: will include all participants who received at least 1 dose of any study drug, have at least 1 evaluable PK sample, and sufficient dosing information.

Biomarker analysis set: will include the subset of participants from the ITT population from whom a valid assay result has been obtained.

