GCP	good clinical practice
GFR	glomerular filtration rate
GGT	gamma-glutamyl transferase
HR	hazard ratio
IB	Investigator's Brochure

ICF	Informed Consent Form
IEC	Independent Ethics Committees
IHC	immunohistochemistry
ILD	interstitial lung disease
IMP	investigational medicinal product (see also “investigational product”): A medicinal product, which is being tested or used as a reference, including as a placebo, in a clinical trial
interim analysis	an analysis of clinical study data conducted before the final reporting database is created/locked
investigational product	A pharmaceutical form of an active ingredient or placebo being tested or used as a reference in a clinical study, including products already on the market when used or assembled (formulated or packaged) in a way different from the authorized form, or marketed products used for an unauthorized indication, or marketed products used to gain further information about the authorized form.
IRB	institutional review board
ITT	Intention-to-treat: The principle that asserts that the effect of a treatment policy can be best assessed by evaluating on the basis of the intention to treat a participant (that is, the planned treatment regimen) rather than the actual treatment given. It has the consequence that participants allocated to a treatment group should be followed up, assessed, and analyzed as members of that group irrespective of their compliance to the planned course of treatment.
IV	intravenous
IWRS	interactive Web response system
medication error	
errors in the prescribing, dispensing, or administration of a study intervention, regardless of whether or not the medication is administered to the participant or the error leads to an AE. Medication error generally involves a failure to uphold 1 or more of the 5 “rights” of medication use: the right participant, the right drug, the right dose, right route, at the right time.
 
In addition to the core 5 rights, the following may also represent medication errors:
 
 • dose omission associated with an AE or a product complaint • dispensing or use of expired medication • use of medication past the recommended in-use date • dispensing or use of an improperly stored medication • use of an adulterated dosage form or administration technique inconsistent with the medication’s labeling (for example, Summary of Product Characteristics, IB, local label, protocol), or • shared use of cartridges, prefilled pens, or both.

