Attachment 5. Protocol JP04 Addendum Restricted and Prohibited Concomitant Therapy

This attachment describes medications, treatments, and drug classes restricted or prohibited, with exceptions and conditions for use during the study treatment period (there are no prohibited therapies during the follow-up period). Participants who, in the assessment by the investigator, require the use of any of the prohibited treatments for clinical management should be removed from the trial. Participants may receive other supportive therapy or vaccinations that the investigator deems to be medically necessary.

Vaccine Guidance

Live vaccines are not permitted while on treatment and for at least 3 months after the last dose of abemaciclib.

Guidance for Modulators of CYP3A

Abemaciclib is extensively metabolized through oxidation by CYP3A. In clinical drug interaction studies,

- coadministration of clarithromycin, a strong CYP3A inhibitor, increased exposure (AUC) of abemaciclib by 3.4-fold (Study I3Y-MC-JPBE), and
- coadministration of rifampin, a strong CYP3A inducer, decreased exposure of abemaciclib by 95% (Study I3Y-MC-JPBF).

Strong inhibitors of CYP3A (given via non-topical routes of administration) should be substituted or avoided if possible (see list below). This includes grapefruit or grapefruit juice. In particular, avoid oral administration of the very strong CYP3A inhibitor, ketoconazole.

If coadministration with a strong CYP3A inhibitor is unavoidable, investigators should reduce the dose of abemaciclib according to the dose reduction table in Section 3.7.8.3. For participants receiving the original starting dose, the dose should be reduced to the first dose reduction level. For participants who have already had a dose reduction for tolerability, reduce the dose further to the second dose reduction level. For subjects receiving doses which do not have an appropriate dose reduction option, or who have already been dose reduced to the lowest possible dose level, the investigator may consider suspending abemaciclib for the duration of the strong CYP3A inhibitor medication. Dose suspensions ≥ 21 days must be discussed with Lilly CRP/CRS.

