- After obtaining the necessary signed informed consent from the pregnant female partner directly, the investigator will record pregnancy information on the appropriate form and submit it to the sponsor within 24 hours of learning of the partner's pregnancy. The female partner will also be followed to determine the outcome of the pregnancy. Information on the status of the mother and child will be forwarded to the sponsor. Generally, the follow-up will be no longer than 6 to 8 weeks following the estimated delivery date. Any termination of the pregnancy will be reported regardless of fetal status (presence or absence of anomalies) or indication for the procedure.

Female Participants who become pregnant

- The investigator will collect pregnancy information on any female participant who becomes pregnant while participating in this study. Information will be recorded on the appropriate form and submitted to the sponsor within 24 hours of learning of a participant's pregnancy.
- The participant will be followed to determine the outcome of the pregnancy. The investigator will collect follow-up information on the participant and the neonate and the information will be forwarded to the sponsor. Generally, follow-up will not be required for longer than 6 to 8 weeks beyond the estimated delivery date. Any termination of pregnancy will be reported, regardless of fetal status (presence or absence of anomalies) or indication for the procedure.
- While pregnancy itself is not considered to be an AE or SAE, any pregnancy complication or elective termination of a pregnancy will be reported as an AE or SAE. A spontaneous abortion is always considered to be an SAE and will be reported as such. Any post-study pregnancy related SAE considered reasonably related to the study intervention by the investigator will be reported to the sponsor as described in Section 9.2.1 of the CAMPFIRE Master Protocol. While the investigator is not obligated to actively seek this information in former study participants, he or she may learn of an SAE through spontaneous reporting.

Any female participant who becomes pregnant while participating in the study will discontinue study intervention and be withdrawn from the study.

Attachment 8. Protocol JP04 Addendum Provisions for Changes in Study Conduct During Exceptional Circumstances

Implementation of this appendix

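### Two rules end study participation, not only treatment, so later PFS and OS go uncollected for pregnant participants and, read literally, for those needing prohibited therapy

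*Protocol*

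**What the plan says.** **Pregnancy.** Attachment 7 of the protocol states that a participant who becomes pregnant "will discontinue study intervention and be withdrawn from the study". These are two separate acts. The only follow-up it names afterwards concerns the pregnancy: "The participant will be followed to determine the outcome of the pregnancy".

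**Prohibited therapy.** Attachment 5 states that participants who, in the investigator's assessment, "require the use of any of the prohibited treatments for clinical management should be removed from the trial". The sentence before it limits the restrictions to the treatment period and adds that "there are no prohibited therapies during the follow-up period". Section 3.7.6, which points to Attachment 5 for the list, bars other anticancer drugs during study treatment: "No other chemotherapy, investigational medications, immunotherapy, hormonal cancer therapy, herbal supplements and/or herbal drugs intended to treat cancer will be permitted".

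**Follow-up after treatment stops.** Section 3.2 says: "Tumor assessments should continue approximately every 3 months during follow-up for participants without evidence of disease progression at the time of treatment discontinuation". Table JP04.3 keeps survival status and later anticancer therapy under collection. Under Section 3.2 and footnote d of that table, long-term follow-up stops at death, at withdrawal from the study or at study completion.

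**Intention to treat.** Attachment 1 defines the principle to mean that participants "should be followed up, assessed, and analyzed as members of that group irrespective of their compliance to the planned course of treatment". Section 3.10.2 says of the ITT set: "This analysis set will be used for all baseline and efficacy analyses".

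**The concern.** Stopping study treatment and leaving the study are different events. After the first, the protocol goes on looking for progression and death. After the second, it does not. Both rules are worded as the second, although nothing about pregnancy or a prohibited drug prevents survival status from being recorded.

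At stake is whether the resulting censoring is independent of outcome. The plausible problem case is a participant who deteriorates clinically, has no progression yet by blinded independent review, and needs other chemotherapy. If that need removes the participant from the trial, a likely imminent event becomes a censored observation. The trial is open-label, so decisions to change therapy are made with knowledge of the arm.

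**Working it through.** The plan gives no figure to reproduce on this point. Power, alpha, the hazard ratio and the event count in Section 3.10.1 are redacted. The check is mainly textual, with arithmetic for scale.

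**Step 1: what removal does to the endpoints**

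- Withdrawal from the study ends long-term follow-up (Section 3.2; Table JP04.3, footnote d).
- PFS is then censored at the last adequate tumor assessment (Protocol Section 3.10.3.1.1; SAP Section 7.7.1.1).
- OS is censored at the last date known alive (SAP Section 7.7.2).
- The study-discontinuation reasons in SAP Section 7.2 name neither pregnancy nor prohibited therapy. The sensitivity analyses in SAP Section 7.7.1.8 do not address such removals.

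**Step 2: the two rules against the rest of the protocol**

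| Rule or statement | Follow-up for progression and survival |
|---|---|
| Attachment 7, pregnancy | Ends with withdrawal from the study |
| Attachment 5, need for prohibited therapy | Ends, if removal from the trial is taken literally |
| Attachment 5, preceding sentence | Assumes a follow-up period in which nothing is prohibited |
| Section 3.2 and Table JP04.3 | Continues after treatment stops |
| Attachment 1, ITT definition | Continues irrespective of compliance |

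The first two rows conflict with the last two. The second row also sits badly with the third: a follow-up period without prohibitions has little purpose if a participant who needs such a therapy has already left the trial.

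**Step 3: why the loss can be informative**

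The PFS censoring table (Table JP04.7 in the protocol, Table JP04.7.1 in the SAP) has no rule that censors at the start of new anticancer therapy. Subject to its rule on missed scans, progression after such therapy therefore counts as an event when the participant is still followed. Table JP04.3 also asks for imaging within 4 to 6 weeks when treatment stops for clinical progression without objective confirmation. Removal under Attachment 5 before that scan would turn the possible event into censoring.

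**Step 4: scale**

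Inputs: at least 45 participants, randomized 2:1 (Section 3.10.1).

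- Arm A: 45 × 2/3 = 30. Arm B: 45 × 1/3 = 15.
- One participant: 1/45 = 2.2% of the trial, 1/30 = 3.3% of Arm A, 1/15 = 6.7% of Arm B.

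**Step 5: power, for orientation only**

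The Schoenfeld approximation, frequentist and without the historical controls, is power = Φ(√(E × 2/3 × 1/3) × |ln HR| − z₁₋α). The assumed ranges, not taken from the documents, are one-sided α 0.025 to 0.20, HR 0.5 to 0.7, and E = 30 to 42 events.

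- Example with α = 0.025, HR 0.5, E = 30: √6.667 × 0.693 − 1.960 = −0.170, so power is 0.432. With E = 27: √6 × 0.693 − 1.960 = −0.262, so power is 0.397. The loss is 3.6 percentage points.
- Over the whole grid, losing 1, 2 or 3 events costs about 0.4 to 1.2, 0.7 to 2.4 or 1.1 to 3.6 points.

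The primary analysis is triggered by an event count. If it waits for that count, later events replace the lost ones, and the remaining issue is bias rather than power.

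**The case against.** The best case against the point is that removal from the trial in Attachment 5 means removal from treatment. The surrounding text is about the treatment period. Section 3.2 has all participants enter long-term follow-up after the short-term visit. Table JP04.3 collects later therapy for everyone, and its footnote a stops procedures only when consent is withdrawn. Section 3.8 leaves discontinuation criteria to the CAMPFIRE Master Protocol, which is not among the documents and may separate the two kinds of discontinuation. This stands as a reason to call Attachment 5 ambiguous. It does not rescue Attachment 7, which names treatment and study separately and ends both.

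The reach is also narrow. Palliative radiation and surgery may be allowed (Section 3.7.6), resection of a tumor that becomes operable is allowed (Section 3.7.8.1.1), and many participants who need new anticancer therapy will already have progressed. That also stands.

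Three stronger readings are tempting, and the documents do not support them:

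- **That Attachment 7 contradicts itself by following the pregnancy after withdrawal.** Following a pregnancy to its outcome is safety reporting. The same attachment asks for it in female partners, who were never participants, and it provides for reports on former participants. The two statements are compatible.
- **That CYP3A guidance causes more removals in Arm A.** CYP3A modulators are restricted, not prohibited. Attachment 5 gives a route for unavoidable strong inhibitors, asks for discussion of longer inducer use, and says its table does not rule out clinically indicated use.
- **That a definite number of participants will lose their outcomes.** A reader might assume that 5% to 10% need a prohibited therapy and arrive at 2 to 5 of 45. Nothing in the documents supports such a rate.

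**Conclusion.** The point holds in a limited form. Attachment 7 plainly ends endpoint follow-up for a pregnant participant, and Attachment 5 does so on a literal reading. Both conflict with the ITT definition and with the off-treatment schedule. A reader might infer that these participants drop out of the analysis altogether. They do not: all randomized participants remain in the ITT set, events before removal count, and only outcomes after removal are lost.

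The number affected is likely to be small and cannot be derived from the documents. Pregnancy is probably rare here. The case that matters more is need for other anticancer therapy before progression by blinded review. This rests on two assumptions: that the therapies barred in Section 3.7.6 count as prohibited treatments under Attachment 5, and that such need is related to prognosis. The direction of any bias in the hazard ratio cannot be stated, because it depends on which arm has more removals. In groups of 30 and 15, a few informative censorings are still worth avoiding when the remedy is so cheap.

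**What to change.** Reconcile Attachments 5 and 7 with Section 3.2, Table JP04.3 and the ITT definition in Attachment 1. Add one sentence to each of the two attachments: after the event, survival follow-up continues, and scheduled tumor assessment continues where feasible, unless the participant withdraws consent. Check the wording against the discontinuation section of the master protocol, to which Section 3.8 refers. When treatment should stop is left to the sponsor and investigators.

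The cost is two sentences at the next amendment. The visits already exist in Table JP04.3, which accepts telephone contact for information on later therapy, so no new procedure is needed.

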Attachment 9. Protocol JP04 Addendum Country-specific Requirements

The country-specific addendum reflected in this appendix must be performed in the respective country, in addition to all procedures required by current version of Protocol J1S-MC-JP04 (JP04) where applicable. The consolidation of this country-specific addendum into this appendix is to facilitate transition of this trial to the CTIS system under the new clinical trial regulation (CTR) in Europe.

Germany

This addendum is to address feedback from the Federal Institute for Drugs and Medical Devices (BfArM) in Germany.

The revised text in the following sections shows the changes applicable only to participants in Germany. All deletions have been identified by ~~strikethroughs~~; all additions have been identified by the use of underline.

Protocol Section 3.2. Schedule of Activities

Investigators will provide age-appropriate explanations to all children prior to any assessment or procedure. Investigators should assess and monitor physical pain and distress at each visit.

[figure not shown]
[figure not shown]

Protocol Section 3.6.1. Inclusion Criteria

[35] Participants aged ~~4~~ to <40 years

Attachment 2. Protocol JP04 Addendum Clinical Laboratory Tests

Table JP04.8 below shows the estimated blood volumes per visit, specified per age group and sex. These blood volumes are within the ranges established in the Ethical considerations for clinical trials on medicinal products conducted with minors (EU 2017).

Table JP04.8 Study JP04 Estimated Blood Volume Per Visit (mL)

Baseline^a		Cycle 1 Day 1		Cycle 1 Day 8		Cycle 1 Day 15		Cycle 2 Day 1	
< 10 years	≥ 10 years	< 10 years	≥ 10 years	< 10 years	≥ 10 years	< 10 years	≥ 10 years	< 10 years	≥ 10 years
									
Cycle 2 Day 8		Cycle 2 Day 15		Cycle 3 Day 1		Cycle 3 Day 8		Cycle 3 Day 15	
< 10 years	≥ 10 years	< 10 years	≥ 10 years	< 10 years	≥ 10 years	< 10 years	≥ 10 years	< 10 years	≥ 10 years
									
Cycle 4 Day 1		Cycle 4 onward Day 8		Cycle 4 onward Day 15		Cycle 5 onward Day 1		Visit 801	

≤ 10 years	≥ 10 years	≤ 10 years	≥ 10 years	≤ 10 years	≥ 10 years	≤ 10 years	≥ 10 years	≤ 10 years	≥ 10 years
■	CCI ■	■	■	■	■	■	■	■	■

Abbreviations: C1D1 = Cycle 1 Day 1; f = female; m = male; mL = milliliter; PK = pharmacokinetics; WOCBP = women of childbearing potential.

^a Baseline collections are represented in Table JP04.8 as a single collection volume though tests may be collected separately on different days as shown in Protocol Table JP04.1 Baseline Schedule of Activities in J1S-MC-JP04 Clinical Protocol Addendum.

CCI

Haematology and clinical chemistry collections to occur ≤14 days relative to C1D1. Labs drawn within 7 days of C1D1 can be used for both baseline and C1D1.

Serum pregnancy collection to occur ≤14 days relative to C1D1.

Blood volumes for haematology, clinical chemistry, pregnancy, and CCI are estimates as these are performed locally.

Treatment collections:

Cycle X Day 1: Haematology and clinical chemistry collections to occur ≤3 days before starting a new cycle of therapy.

Cycle X Day 8 and 15: Haematology and clinical chemistry collections have visit interval tolerance of ±3 days.

Cycle 1 Day 1: Exploratory biomarker collection, 10 mL for participants ≥10 years of age.

Serum pregnancy: Confirmation only needed if urine test is positive. 1 mL estimated and displayed in table, regardless of WOCBP status for participants ≥10 years of age.

CCI

Visit 801:

- Has visit interval tolerance of ±14 days.

Exploratory biomarker collected only for participants who did not have a sample collected at the time of disease progression or at the time when study treatment was discontinued, additional 10 mL for participants ≥10 years of age.

Potential triggered collections:

Hepatic monitoring triggered for safety reasons with a range of 1.8 mL to 76.3 mL.

Cystatin C triggered for safety reasons, additional 2.5 mL.

Disease Progression: Exploratory biomarker collection, additional 10 mL for participants ≥10 years of age.

Retests, as needed, PK an additional 0.01 to 4 mL.

Reference

[EU] Ethical considerations for clinical trials on medicinal products conducted with minors. Recommendations of the expert group on clinical trials for the implementation of Regulation (EU) No 536/2014 on clinical trials on medicinal products for human use. Rev. 1. Published September 18, 2017. Accessed August 10, 2022.

https://www.ejprarediseases.org/wp-content/uploads/2021/10/EC_ethical-consideration-on-clinical-trials-with-minors_2017.pdf

Spain

This addendum is to address feedback from the Agencia Española de Medicamentos y Productos Sanitarios (AEMPS) in Spain.

The revised text in the following sections shows the changes applicable only to participants in Spain. All deletions have been identified by ~~strikethroughs~~; all additions have been identified by the use of underscore.

